3.4 Subject Selection

The study will randomize approximately 50 subjects into Cohort 1 and approximately 356 subjects into Cohort 2 at a 1:1 ratio of ganaxolone to placebo. It is estimated that approximately 320 subjects will complete the 14-week DB Phase of Cohort 2, which assumes approximately 10% discontinuation rate.

3.4.1 Inclusion Criteria

Subjects must meet all inclusion criteria to be eligible for entry in the study. The option for re-screening of subjects who do not meet all criteria must be discussed with the medical monitor.

1. Able to give informed consent in writing, or have a legally authorized representative able to do so, after being properly informed of the nature and risks of the study and prior to engaging in any study-related procedures.
2. Willing to enter and participate for the full term of either the 9 or 14-week DB phase and willing to enter into the 52-week OL phase.
3. Male or female outpatients ≥ 18 years of age at time of consent.
4. Have a confident diagnosis of drug-resistant epilepsy with POS with or without secondary generalization (classified according to International League Against Epilepsy Guidelines [Guy, 1981] and as determined by secondary review by the Epilepsy Consortium) for ≥ 2 years and is having POS, with or without secondary generalization despite having been treated in the past with ≥ 2 approved anti-epilepsy drugs (AEDs) either alone or in

combination at adequate doses for a sufficient length of time in the opinion of the investigator. Diagnosis should have been established by clinical history, electroencephalogram (EEG) or video EEG with results consistent with partial-onset epilepsy, and computerized tomography (CT) or magnetic resonance imaging (MRI) of the brain to rule out progressive structural lesions within the last 10 years.

5. Based on documented history of POS, the investigator judges that the subject is likely to have 3 or more POS*, with or without secondary generalization, during any 4-week period prior to study treatment, i.e, rarely falls below that threshold with usual fluctuations. Further, the pattern of seizures makes it unlikely the subject will have 21 seizure-free days in any 4-week period prior to study treatment.

* POS includes complex partial seizures [CPS], and simple partial seizures [SPS] with motor expression. Partial seizures may be seizures secondarily generalized [SGTC]. Subjects who only have simple partial seizures without any observable motor component will NOT be eligible to participate in this study.

6. Currently being treated and maintained with a stable regimen of 1, 2, or 3 AEDs for ≥ 1 month prior to the screening visit, without a foreseeable change in dosing for the duration of the DB phase of the study.

Barbituates: If the subject is taking barbiturates (e.g, phenobarbital), the dose of the barbiturate must have been stable for ≥ 3 months prior to the screening visit.

Vagus Nerve Stimulator (VNS): VNS will not be counted towards the number of concomitant AEDs. Subjects with surgically implanted VNS will be allowed to enter the study provided that all of the following conditions are met:

- The VNS has been in place for ≥ 1 year prior to the screening visit
- The settings must have remained constant for ≥ 3 months prior to the screening visit and remain constant throughout the study
- The battery is expected to last for the duration of DB Phase 1 (9 or 14 weeks) of the study

Benzodiazepines: The chronic use of a benzodiazepine as a concurrent AED is permitted as long as the dose has been stable for ≥ 1 month prior to the screening visit and remains constant throughout the study. See Protocol Section 9.4.10 for use of benzodiazepines for seizure rescue or for other indications.

Felbamate: The use of felbamate is allowed provided that the subject has been maintained on a stable dose of felbamate for greater than 18 months, and has had stable liver function (AST/ALT) and hematology during the course of treatment, and is expected to remain constant throughout the study.

Perampanel: The use of perampanel is allowed provided that the subject has been maintained on a stable dose of perampanel for greater than 3 months and has not experienced any serious psychiatric and behavioral reactions such as hostility- and aggression- related adverse reactions.

7. Able and willing to maintain an accurate and complete daily written seizure calendar or has a caregiver who is able and willing to maintain an accurate and complete daily written seizure calendar.
8. Able and willing to take drug with food twice daily. Ganaxolone must be administered with food.
9. Sexually active women of childbearing potential must be using a medically acceptable method of birth control and have a negative qualitative serum β - human chorionic growth

hormone (HCG) pregnancy test from a blood sample collected at the screening visit and negative urine pregnancy tests at baseline line and subsequent visits. A woman of childbearing potential is defined as a female who is biologically capable of becoming pregnant. A medically acceptable method of birth control includes intrauterine devices in place for at least 3 months, surgical sterilization, or adequate barrier methods (e.g, diaphragm and foam). An oral contraceptive alone is not considered adequate for the purpose of this study. Use of oral contraceptives in combination with another method (e.g, a spermicidal cream) is acceptable. In subjects who are not sexually active, abstinence is an acceptable form of birth control and β -HCG will be tested per protocol. Birth control should be continued for a minimum of 3 days after the last dose of study drug.

3.4.2 Exclusion Criteria

1. Have had previous exposure to ganaxolone.
2. Known sensitivity or allergy to any component in the study drug, progesterone, or other related steroid compounds.
3. Exposure to any investigational drug or device less than 30 days prior to screening, or plans to take another investigational drug at any time during the study.
4. Time of onset of epilepsy treatment less than 2 years prior to enrollment.
5. Have generalized epilepsy, such as Lennox-Gastaut syndrome, juvenile myoclonic epilepsy, absence epilepsy, or non-epileptic seizures within the last 12-month period prior to study entry.
6. Have less than 3 POS seizures, with or without secondary generalization, in a 28-day period or more than 21 consecutive seizure-free days during the 8-week baseline period.
7. Have only simple partial seizures without any observable motor component.
8. Have innumerable seizures or status epilepticus within the last 12-months prior to screening.
9. Have more than 100 POS total (complex partial seizures [CPS] only + simple partial seizures [SPS] with motor (both types with or without secondary generalized tonic-clonic seizures [SGTC]) per each 4-week baseline period.
10. Seizures secondary to illicit drug or alcohol use, infection, neoplasm, demyelinating disease, degenerative neurological disease, or central nervous system (CNS) disease deemed progressive, metabolic illness, or progressive degenerative disease.
11. Current use of vigabatrin is not permitted, as well as prior use of vigabatrin without stable visual fields tested twice over the 12 months after the last dose of vigabatrin.
12. Current use of ezogabine (retigabine; Potiga; Trobalt) is not permitted. Subjects who may have used this agent in the past should have been off this medication for at least 3 months prior to screening and should have had a documented normal fundoscopic exam by an ophthalmologist.
13. Are planning surgery, or to be evaluated for surgery, during the 9 or 14-week DB phase to control seizures including those subjects who are considering implantation of a VNS device.
14. Are suffering from acute or progressive neurological disease, moderate or severe psychiatric disease, or severe mental abnormalities that are likely to require changes in pharmacotherapy during the 9 or 14-week DB portion of the study or interfere with the objectives of the study or the ability to adhere to the protocol requirements.
15. Have active suicidal plan/intent, or have had active suicidal thoughts in the past 6 months.

16. Have a history of an actual suicide attempt in the last 5 years or more than 1 lifetime actual suicide attempt as classified by the Columbia-Suicide Severity Rating Scale (C-SSRS).
17. Have a positive urine drug screen at Screening or meet criteria for current or historical Substance Use Disorder (DSM-V criteria) within the past 5 years. As with other AEDs, the use of alcohol is not advised.
18. Have any medical condition that, in the investigator's judgment, is considered to be clinically significant and could potentially affect subject safety or study outcome, including but not limited to: clinically significant cardiac, renal, pulmonary, gastrointestinal, hematologic or hepatic conditions; or a condition that affects the absorption, distribution, metabolism or excretion of drugs.
19. Have Alanine transferase (ALT; SGPT) or Aspartate transferase (AST; SGOT) levels greater than 3 times upper limits of normal (ULN), or total bilirubin greater than 1.5 time ULN at the screening and baseline visits.
20. Have a history of malignancy within the past 2 years, with the exception of basal cell carcinoma.
21. Are currently following or planning to follow a ketogenic diet.
22. Use of dietary supplements or herbal preparations are not permitted if subject has been using them consistently for less than 6 months prior to screening, or does not plan on remaining on stable doses for the duration of the DB phase. Use of St. John's Wort is not permitted (See Protocol Section 9.4.10: Excluded, Prior, and Concomitant Medications).
23. Females who are pregnant, currently breastfeeding or planning to become pregnant during the duration of the study.
24. A history of chronic noncompliance with drug regimens.
25. Inability to withhold grapefruit and grapefruit juice from diet during the entire clinical trial (See Protocol Section 9.4.10: Excluded, Prior, and Concomitant Medications).

3.5 Determination of Sample Size

Using a medium dose (1500 mg/day oral suspension,) the Marinus study 1042-0600 found a mean difference in percentage change in seizure frequency from BL of -19.58%, with a standard deviation of 54.019%. This is equivalent to an effect size of 0.3625. Because a higher dose of ganaxolone (1800 mg/day oral capsule) is used in study 1042-0603, we have assumed an effect size of at least 0.30 can be achieved in Cohort 2. A sample size of 178 in each group has approximately 0.8 power to detect a treatment difference, where the effect size is 0.30, based on Wilcoxon rank sum test with two-sided alpha = 0.05 by using PASS 11 software. Assuming a dropout of 10%, the sample size (160 in each group) will still have a power of approximately 85% to detect an effect size of 0.35. The sample size (178 per group) also provides approximately 88% power when the 50% responder rates are assumed to be 26% for ganaxolone and 13% for placebo, and a large 2 sample Z test is used with the two-sided alpha of 0.05.

3.6 Treatment Assignment & Blinding

Subjects will be randomized to receive ganaxolone or placebo during Phase 1 in a 1:1 ratio by the interactive web response system (IWRS) system. Randomization for Cohort 2 will be stratified by country.

All study medication will be provided as identically appearing gelatin capsules. The contents of each bottle will be blinded using labels that contain a unique bottle number and a manufacturing lot code. The randomization schedule will match a subject number to a bottle number. Upon completion of the 8 week baseline evaluations for each subject, the Investigator, or appropriate designee, will log into the IWRS to randomize the subject to the study drug assignment and receive bottle numbers. The designated personnel at the clinical site will match the assigned bottle numbers with the correct bottles of investigational product and distribute the bottle to the Investigator or designee. Only the investigational product supplier will be unblinded to the bottle number and the contents of each bottle of investigational product. An unblinded representative of the manufacturer will have access to the manufacturing lot codes for active and placebo.

3.7 Administration of Study Medication

All study medication will be provided as identically appearing white/opaque gelatin capsules. Study drug will be packaged in bottles. Ganaxolone or placebo capsules will be administered 2 times daily (BID), following the morning and evening meals. No study-related tests or treatments, including screening, will be conducted before the subject has signed the Informed Consent Form.

3.8 Study Procedures and Flowchart

Figure 1. Cohort 1 Trial Design

[figure not shown]
[figure not shown]

Figure 2. Cohort 2 Trial Design

See Appendix 1: Schedule of Events in the protocol for detailed information regarding the timing of all assessments.

4 ENDPOINTS

4.1 Primary Efficacy Endpoint

The primary efficacy endpoint for US Food and Drug Administration registration is the percent change in the 28-day seizure frequency (POS with or without secondary generalization) from baseline to the DB phase for Cohort 2. Frequency of POS, with or without secondary generalization, for primary and secondary efficacy endpoints only includes 3 seizure subtypes that are SPS-motor, CPS and SGTC. Per patient 28-day seizure frequency will be based on the number of seizures in the Cohort 2 14-week titration + maintenance period of the DB Phase, relative to the 8-week prospective baseline period of the Cohort 2 DB Phase, per 28 days. It will be calculated as the number of seizures over the time interval divided by the number of days with available seizure data in the interval and multiplied by 28 to obtain both the baseline 28-day seizure frequency and the post-baseline 28-day seizure frequency.

The primary efficacy endpoint for European Medicines Agency registration is 50% responder rate during the maintenance treatment period of the DB phase for Cohort 2. A 50% responder is an individual who experiences at least a 50% decrease in seizure frequency compared to baseline. This end-point is analysed independently of the US registration end-point. The key-secondary end-point analysis (below) is not predicated on the results of this end-point.

4.2 Secondary Efficacy Endpoints

Key Secondary Endpoints:

The 3 key secondary endpoints will be tested using a fixed sequence procedure to protect the familywise error rate at 0.05. If the primary outcome measure is statistically significant, the p-values of the secondary measures will be examined in the order listed below. The process stops at the first p-value above 0.05.

- Responder rate (experiencing a $\geq 50\%$ reduction) during the titration + maintenance treatment periods of the DB phase for Cohort 2
- Change in the number of seizure free days per 28-day period from baseline during the titration + maintenance treatment periods of the DB phase for Cohort 2
- Clinical Global Impression of Change – Improvement (CGI-I; Investigator) at Week 14 of the double blind treatment phase relative to the baseline for Cohort 2

All remaining secondary efficacy endpoints listed in the protocol will be tested at $\alpha = .05$ so all p-values are nominal.

Secondary efficacy outcome measures are listed below.

- a) Percent change in the 28-day seizure frequency from baseline to the DB phase during the maintenance treatment period for Cohort 2
- b) Change from baseline in 28-day seizure frequency during the DB phase for Cohort 2 (titration + maintenance and maintenance only).
- c) Change in the number of seizure free days per 28-day period from baseline during the maintenance treatment period of the DB phase for Cohort 2
- d) Proportion of responders experiencing a $\geq R\%$ reduction from baseline to the end of treatment period in 28-day seizure frequency (titration + maintenance and maintenance only) for Cohort 2. R% will be 20%, 40%, 60%, and 80%
- e) Proportion of subjects who completed the DB portion of the study (Cohort 2) and did not experience any seizures during the maintenance phase of the study
- f) Proportion of subjects who experienced at least one 28-day seizure free period during the DB phase of the study (titration + maintenance) for Cohort 2
- g) Longest period of time seizure free (%) (longest period of seizure free days divided by number of days with available seizure data) during the double blind phase (titration + maintenance) for Cohort 2
- h) Change from baseline in 28-day seizure frequency for different subtypes of seizures during the DB portion of the study (titration + maintenance) for Cohort 2 (SPS, SPS-motor, CPS, SGTC)
- i) Patient Global Impression of Change – Improvement (PGI-I; Patient/Caregiver) at each assessment visit
- j) Clinical Global Impression of Change – Improvement (CGI-I; Investigator) at each assessment visit

Exploratory endpoint

[REDACTED] except that the primary endpoint and 50% responder rate will be analyzed the same way as in Cohort 2.

The other primary and secondary efficacy outcome measures will be assessed descriptively for each of the time periods listed below in Cohort 1 DB phase ([a-e] below) and Cohort 1+Cohort 2 OL ([f below]):

- a) Ganaxolone Titration + Maintenance 1200 mg/day + Maintenance 1800 mg/day vs Placebo (Cohort 1: Weeks 1 to 9).
- a) Ganaxolone Maintenance 1200 mg/day + Maintenance 1800 mg/day (Cohort 1: Weeks 2-9) vs Placebo (Cohort 1: Weeks 1 to 9).
- b) Ganaxolone Titration + Maintenance 1200 mg/d (Cohort 1: Weeks 1-5) vs placebo (Cohort 1: Weeks 1 to 9).
- c) Ganaxolone Maintenance 1800 mg/d vs (Cohort 1: Weeks 6-9) placebo (Cohort 1: Weeks 1 to 9).
- d) Ganaxolone maintenance 1200 mg/d vs placebo (Cohort 1: Weeks 2 to 5).
- e) OL (Cohort 1: Weeks 10 to 61; Cohort 2: Weeks 16 to 66).

4.3 Safety Endpoints

Planned safety assessments include:

- Neurological and physical examinations
- Clinical laboratory tests
- 12-lead ECG
- Vital signs: temperature, blood pressure, pulse rate, respiration rate, height, weight and BMI
- AEs: incidence, frequency, severity, duration, causality, outcome

See Protocol Appendix 1 for a Schedule of Events for timing of safety assessments.

Additional safety outcome measures include those listed below:

- Number of subjects at each dose
- Change from baseline in vital signs (blood pressure, respiration rate and heart rate), body weight and ECG
- Assessment of suicidality via the Columbia Suicide C-SSRS

In addition, tolerability of ganaxolone during the up-titration periods of the study will be compared between the 2 cohorts. Cohort 1 went through a 1-week titration period, followed by a 4-week period at 1200 mg/day, before the start of a 4-week treatment with 1800 mg/day. In comparison, Cohort 2 was treated with a 2-week titration period followed by maintenance treatment with 1800 mg/day. AEs with onset during the titration period in Cohort 2 will be compared to AEs with onset during the weeks 1-5 in Cohort 1 (1 week titration + 4 week treatment with 1200 mg/day). In addition, in Cohort 2, AEs with onset during the titration period will be compared to AEs with onset during the maintenance period. AEs that emerge during the de-escalation period will also be tabulated to investigate whether discontinuation of ganaxolone is associated with withdrawal symptoms.

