9.5.3 Safety Assessments

Planned safety assessments include:

Neurological and physical examinations

Clinical laboratory tests

12-lead ECG

Vital signs including temperature, blood pressure, pulse rate, respiration rate, height, weight and BMI

Columbia Suicide Severity Rating Scale (C-SSRS)

AE monitoring: frequency, severity, duration, causality, outcome

Clinical labs, vitals and ECG measurements may be repeated if needed to corroborate or refute abnormal findings. Both the original and replicate assessments should be recorded in the eCRF.

See [Appendix 1](#) Schedule of Events for timing of Safety Assessments.

Adverse events will be presented for these time periods for Cohorts 1 & 2: ganaxolone vs placebo Titration + Maintenance (Cohort 1: Weeks 1-9, Cohort 2: Weeks 1-14), 1200

mg/d vs placebo (Cohort 1: Weeks 2-5), and 1800 mg/d vs placebo (Cohort 2: Weeks 6-9) for the safety population; open-label (Cohort 1: Weeks 10-61, Cohort 2: 15-66). In addition, tolerability of ganaxolone during the up-titration phases of the study will be compared between the two cohorts. AEs with onset during the titration phase in Cohort 2 will be compared to AEs with onset during the weeks 1-5 in Cohort 1 (1 week titration + 4 week treatment with 1200 mg/day). In addition, in Cohort 2, AEs with onset during the titration phase will be compared to AEs with onset during the maintenance phase. AEs that emerge during the de-escalation period will be tabulated to investigate whether discontinuation of ganaxolone is associated with withdrawal symptoms. Secondary safety outcome measures include those listed below.

Secondary Safety Parameters for Cohorts 1 & 2	Cohort 1		Cohort 2		Combine Cohorts 1 & 2	
	DB Phase	OL Phase	DB Phase	OL Phase	DB Phase	OL Phase
Number of subjects at each dose	X	X	X	X		X
The frequency and proportion of subjects with AEs	X	X	X	X		X
Severity of AEs	X	X	X	X		X
AEs leading to DC	X	X	X	X		X
Incidence of subjects with early DC	X	X	X	X		X
Change from baseline in vital signs (blood pressure, respiration rate and heart rate), body weight and ECG	X	X	X	X		X
Change in clinical hematology and chemistry parameters	X	X	X	X		X
Assessment of suicidality via the Columbia Suicide Severity Rating Scale (C-SSRS)	X	X	X	X		X

Additional assessments may be conducted as considered appropriate.

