Between DB (Phase 1) and OL (Phase 2) study phases, Cohort 1 has a 1-week, double-blinded, step transition for placebo subjects to 900 mg/d followed by 1800 mg/d while ganaxolone subjects are maintained on their current dose. For the purpose of entering dosing information on the eCRFs, the sites are instructed to assume that all patients transitioning to the OL phase are on placebo and will enter dose-escalation information accordingly. After unblinding K&L will correct the actual dosing, and the patients who were on ganaxolone during the DB phase will be changed to have received 1800 mg/day during the transition period.

Cohort 1, Phase 2 is the OL phase, consisting of 2 treatment phases: Flexible Dosing (51-week flexible dosing during which time the dose may be adjusted based on efficacy and tolerability guidelines), and De-escalation (2 weeks, at study termination). Subjects discontinued during the study will be de-escalated over 2 weeks based on dose, duration, and tolerability in the opinion of the investigator.

Cohort 2, Phase 1 of treatment includes a 14-week DB phase placebo-controlled treatment period to evaluate oral study medication as add-on therapy in adults with epilepsy consisting of POS, with or without secondary generalization. Study subjects will be randomized to one of the 2 study treatment arms: ganaxolone at 1800 mg/d or placebo. Phase 1 (DB phase) is comprised of a Baseline period (8 weeks), followed by 2 treatment periods: Titration (2 weeks up to 1800 mg/d) and Maintenance (12 weeks on 1800 mg/d). Subjects entered into Cohort 2, under

Protocol Amendment 2, will have a baseline assessment based on 4 weeks retrospective and 4 weeks prospective seizure data.

Between the study phases, Cohort 2 has a 2-week, blinded, step transition for placebo subjects to ganaxolone, starting at 900 mg/d to 1800 mg/d, while ganaxolone subjects are maintained on their current dose. For the purpose of entering dosing information on the eCRFs, the sites are instructed to assume that all patients transitioning to the OL phase are on placebo and will enter dose-escalation information accordingly. After unblinding K&L will correct the actual dosing, and the patients who were on ganaxolone during the DB phase will be changed to have received 1800 mg/day during the transition period.

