9.3 Adverse Events

The summary of AEs (or SAEs) will be limited to treatment emergent adverse events (TEAEs). A TEAE is any AE (or SAE) occurring on or after administration of the first dose of study medication and before the end of study. An existing AE which worsens on or after administration of the first dose of study medication is also considered a TEAE. AEs will be tabulated by treatment and Overall, system organ class (SOC), and Preferred Term using the MedDRA v.16.0 coding system. The number and percentage of subjects with adverse events will be calculated for each cohort in each phase of the study, by treatment and overall, and in Cohort 1 DB phase, by dose and overall. Additional tables with AEs subset by severity and by relationship to drug as assessed by the investigator will also be presented. Subset listings will be

produced for adverse events that cause withdrawal and for SAEs. Any AE with completely missing start and end dates will be considered a TEAE.

All necessary information about an AE (onset, duration, severity, seriousness, causality to study drug, action taken, and outcome) should be documented by the investigator on the adverse event eCRFs (AE eCRFs). Minimum information required for each AE includes type of event, duration (start and end dates), severity, seriousness, causality to study drug, action taken, and outcome.

Severity of AEs will be graded by the Investigator using the following criteria as guidelines:

1. Mild: Nuisance, barely noticeable.
2. Moderate: Uncomfortable, troublesome symptoms not significantly interfering with daily activities or sleep.
3. Severe: Symptoms significantly interfere with daily activities or sleep.

The relationship of the AE to the study drug should be specified by the Investigator, using the following definitions:

1. Not Related: Concomitant illness, accident or event with no reasonable association with study drug.
2. Unlikely Related: The event has little or no temporal sequence from administration of the study drug, and/or a more likely alternative etiology exists.
3. Possibly Related: The event follows a reasonable temporal sequence from administration of study drug but which could also be explained by concurrent disease or other factors or medications.

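### The planned up-titration tolerability comparisons use windows of unequal length and different dose path, so neither can be separated from the titration schedule

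*SAP*

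**What the plan says.** SAP 4.3 gives the purpose: "tolerability of ganaxolone during the up-titration periods of the study will be compared between the 2 cohorts". It then defines the contrast: "AEs with onset during the titration period in Cohort 2 will be compared to AEs with onset during the weeks 1-5 in Cohort 1". Protocol 9.5.3 has the same contrast: "AEs with onset during the titration phase in Cohort 2 will be compared to AEs with onset during the weeks 1-5 in Cohort 1". A second contrast follows in both documents; in the SAP it reads "in Cohort 2, AEs with onset during the titration period will be compared to AEs with onset during the maintenance period".

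On the statistic, SAP 9.3 says "The number and percentage of subjects with adverse events will be calculated for each cohort in each phase of the study". The same section lists onset-window tables by preferred term: Cohort 1 Weeks 1-5 and Weeks 6-9, and Cohort 2 titration and maintenance. Those entries name no statistic of their own. SAP 9.1 summarises days on drug but does not link them to AEs. Neither document plans a person-time rate, a matched window, a time-to-onset analysis or a formal test for these contrasts.

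**The concern.** The share of subjects with at least one AE cannot fall as the observation window lengthens. Comparing 35 days in one cohort with 14 in the other therefore mixes time at risk with the thing of interest, which is how well each titration schedule is tolerated.

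The windows also stop at different points on the dose path. The Cohort 2 window takes in the arrival at 1800 mg/d. The Cohort 1 window ends just before that cohort's own step to 1800 mg/d, which Protocol Table 1 itself labels as a titration step. At 600 mg/d it is the largest single rise in either double-blind schedule; the others are 400 or 450 mg/d. Protocol section 7 describes AE incidence in an earlier study as dose-related, so where the window stops could matter.

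The two features pull in opposite directions. The longer window can make the Cohort 1 schedule look worse, and leaving out its step to 1800 mg/d can make it look better. A reader of the finished table could not tell how much of any difference came from either. Safety and tolerability against placebo is a secondary objective, and this is the plan's stated comparison of the two up-titration schedules.

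**Working it through.** **Window lengths (Protocol Tables 1 and 2).**
- Cohort 1 Weeks 1-5: Days 1-35, 35/7 = 5 weeks. The step to 1800 mg/d is on Day 36.
- Cohort 2 titration: Days 1-14, 14/7 = 2 weeks. 1800 mg/d starts on Day 11, so Days 11-14 are at that dose.
- Cohort 2 maintenance: Days 15-98, 98 - 15 + 1 = 84 days, 84/7 = 12 weeks.

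These reproduce the 5-, 2- and 12-week periods that the documents state. The length ratios are 5/2 = 2.5 and 12/2 = 6.

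**Model.** The expected percentage of subjects with an onset in a window is 1 - exp(-H), where H is the hazard summed over the weeks of the window. *No true difference* means the same weekly hazards in both cohorts. The shape of the hazard is an assumption, because the documents give no onset times.

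**Constant hazard at an AE rate from the documents.** Protocol section 7 gives dizziness in 16.3% of ganaxolone subjects in the earlier 10-week study. Assuming those events accrued evenly over the 10 weeks, h = -ln(1 - 0.163)/10 = 0.0178 per week.
- 2 weeks: 1 - exp(-0.0178 × 2) = 3.5%
- 5 weeks: 1 - exp(-0.0178 × 5) = 8.5%, ratio 2.43 from unrounded values
- 12 weeks: 1 - exp(-0.0178 × 12) = 19.2%, ratio 5.50

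For the rarest rate given (somnolence on placebo, 2.0%) the ratios are 2.49 and 5.94, close to the limits of 2.5 and 6.

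**Hazard falling over time.** Let the weekly hazard be multiplied by r each week, scaled so that 20% have an onset in the first 2 weeks (an assumption). The maintenance column uses Weeks 3-14.

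| r | 5-week % | Ratio to 2 weeks | Maintenance % | Ratio to titration |
|---|---|---|---|---|
| 1 (constant) | 42.8 | 2.14 | 73.8 | 3.69 |
| 0.9 | 38.2 | 1.91 | 49.5 | 2.47 |
| 0.75 | 32.2 | 1.61 | 24.3 | 1.21 |
| 0.5 | 25.0 | 1.25 | 7.2 | 0.36 |
| 0.25 | 21.2 | 1.06 | 1.5 | 0.07 |
| 0 (all in week 1) | 20.0 | 1.00 | 0 | 0 |

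Worked line for r = 0.5: the weights sum to 1.5 over Weeks 1-2, 1.9375 over Weeks 1-5 and 0.50 over Weeks 3-14. The first-week hazard is -ln(0.8)/1.5 = 0.1488. So the 5-week figure is 1 - exp(-0.1488 × 1.9375) = 25.0%, and maintenance is 1 - exp(-0.1488 × 0.50) = 7.2%.

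**What could be hidden.** Under a constant hazard, the two cohorts show equal percentages when Cohort 2's weekly hazard is 2.5 times Cohort 1's. For example, 1 - exp(-0.05 × 5) = 22.1% and 1 - exp(-0.125 × 2) = 22.1%.

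**Precision.** Protocol section 2 gives about 46 subjects in Cohort 1 at 1:1, so about 23 on ganaxolone (25 if SAP 3.3's figure of about 50 is used). At a true 20%, the standard error is √(0.2 × 0.8/23) = 8.3 percentage points, or roughly ±16 points at 95%.

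**The case against.** The case for leaving the plan alone has several good parts.

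- **Dose-path logic.** Weeks 1-5 are the whole of Cohort 1's time before 1800 mg/d. That is an intelligible choice, though the SAP does not explain it, and the windows are stated openly.
- **Descriptive use.** No test, alpha or decision rule depends on the comparison, and Cohort 1 is small.
- **The Cohort 1 step is reported elsewhere.** A reader might infer that AEs after Day 36 go unreported. They do not: SAP 9.3 plans a Cohort 1 table for Weeks 6-9, which is Days 36-63. They are only missing from the between-cohort contrast.
- **Placebo is shown.** A reader might infer that placebo is ignored. SAP 9.3 summarises AEs by treatment group within each cohort and phase, and Protocol 9.5.3 lists ganaxolone against placebo. A placebo column over the same window would help to expose inflation from window length. What is missing is a statement that these particular contrasts are to be read against it.
- **The statistic is inferred.** Use of percentages for the onset-window tables is a reasonable reading of SAP 9.3, but the entries do not say so, and the table shells are in a separate file.

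It is also tempting to say that the cohorts were enrolled one after the other. The documents do not state this. What they do show is that randomisation is to ganaxolone or placebo and not to cohort.

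All of this limits the weight of the point. None of it makes a 14-day window comparable with a 35-day window that stops at a different place on the dose path.

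**Conclusion.** The concern holds as confounding: window length and dose path cannot be separated from titration schedule in the contrasts as planned. With no true difference, the between-cohort percentage ratio could be anywhere from about 1.0 (all onsets in week 1) to about 2.5 (constant low hazard). The maintenance-to-titration ratio could run from below 1 to about 6. Both ranges rest on a weekly hazard that is constant or falling and equal in the two cohorts. A hazard that rises with dose was not modelled and could take the ratios higher.

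Two stronger readings are not supported. One is that window length, rather than titration speed, determines the result. The other is that maintenance will nearly always show more AEs than titration. Each needs a near-constant hazard, which nothing in the documents establishes. If onset is strongly front-loaded (r = 0.5 or less), the 5-versus-2-week distortion is 1.25 or smaller and titration shows more AEs than maintenance.

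Because the comparison is descriptive and rests on about 23 ganaxolone subjects in Cohort 1, this is an inexpensive improvement to a secondary safety display. It does not threaten the trial's main conclusions.

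**What to change.** Amend SAP 4.3 and 9.3 and Protocol 9.5.3 as follows.

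1. Base the between-cohort comparison on equal windows from first dose: Days 1-14 and Days 1-63 in both cohorts. Days 1-63 covers the full path to 1800 mg/d in each.
2. Add new-onset AEs in the first 28 days at 1800 mg/d: Cohort 1 Days 36-63 (63 - 36 + 1 = 28) and Cohort 2 Days 11-38 (38 - 11 + 1 = 28). State the denominator and how many subjects left before reaching that dose.
3. Add time-to-first-AE curves by week from first dose.
4. For Cohort 2 titration versus maintenance, show first-onset AEs by week among subjects still at risk, in place of one percentage per period. A single person-week rate per period is not enough, because under a falling hazard it still differs between windows of unequal length.
5. Show each display beside the same cohort's placebo arm over the same window, since subjects are not randomised between cohorts.
6. Keep the planned tables as supportive.

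The cost is SAP and protocol wording plus a few extra tables and figures. AE onset dates and dosing dates are already collected, and no dose, visit or clinical rule changes.
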